2.3 RISK/BENEFIT ASSESSMENT

2.3.1 KNOWN POTENTIAL RISKS

The risks primarily involve direct adverse effects of duloxetine which are well-described and minimal (i.e., sedation, nausea, headache, and dizziness that are typically transient in nature) in most individuals. For those who do not tolerate the side effects, the medication will be reduced or discontinued with an appropriate 7-day tapering regimen to prevent discontinuation syndrome. Side effects of these medications resolve shortly after stopping them.

Pregnant women are excluded from participation in this study. Because NO method of birth control is 100% reliable, a pregnancy test is required at baseline and at week 13. For subjects who become pregnant while in the study, duloxetine will be discontinued (with appropriate tapering regimen), and subjects will be allowed to continue with the study.

If a participant happens to become pregnant while in the study, the **rare** side effects of duloxetine for the fetus late in the third trimester include breathing difficulties, seizures, temperature instability, feeding difficulty, vomiting, low blood sugar, jitteriness, irritability, and tremor. To avoid unnecessary exposure to duloxetine, participants will get a repeat urine pregnancy test mid-way (week 13) during the 24 week study period. The enumerated side effects are side effects for the newborn.

Other potential risks include emotional distress related to the web-based pain coping skills training, which is typically a minor issue. Our trained research assistant, who collects information on medication

side effects, will be able to ask about emotional distress, with an agreed upon approach to refer participants to the medical safety officer if any concerns are present. Participants should discuss the risk of being in this study with the study staff.

There are no additional tests performed while enrolled in this study; however, a participant's study doctor may capture results of testing performed for normal clinical care.

Taking part in this research study may involve providing information that a participant considers confidential or private. Efforts, such as coding research records, keeping research records secure and allowing only authorized people to have access to research records, will be made to keep information safe.

2.3.2 KNOWN POTENTIAL BENEFITS

Participants may experience relief of pain and improvement in quality of life. It is possible; the information learned from this study will benefit other people in the future.

2.3.3 ASSESSMENT OF POTENTIAL RISKS AND BENEFITS

See Section 2.3.1, Known Potential Risks, and Manual of Procedures (MOP) chapter 05, Informed Consent for more details regarding potential risks and benefits.

3 OBJECTIVES AND ENDPOINTS

OBJECTIVES	ENDPOINTS	JUSTIFICATION FOR ENDPOINTS

Primary
 
The primary outcome of the study is BPI GPS score collected at Weeks 13 and 25. BPI GPS is a self-report measure of pain severity and interference with proven reliability and validity across different pain conditions. It is defined as the average of BPI pain severity and BPI pain interference. BPI pain severity is the average of 4 items asking about current pain and worse, least, and average pain in the past week. BPI pain interference is the average of 7 items that rate how pain interferes with various activities (higher score indicate greater pain interference). We have two
	
Brief Pain Inventory-Global Pain Severity.
	
BPI GPS is a self-report measure of pain severity and interference with proven reliability and validity across different pain conditions^{1,2}. In this application, BPI GPS is defined as the average of BPI pain severity and BPI pain interference. BPI pain severity is the average of 4 items asking about current pain and worse, least, and average pain in the past week. BPI pain interference is the average of 7 items that rate how pain interferes with various activities (higher score indicate greater pain interference)⁵⁹.

OBJECTIVES	ENDPOINTS	JUSTIFICATION FOR ENDPOINTS
primary hypotheses (H1 and H2): H1: Combination treatment with and without health care professional support is more effective than duloxetine monotherapy in improving GPS. H2: Combination treatment with health care professional support is more effective than combination treatment without health care professional support in improving GPS. For further details, see section 9.4.2, Analysis of the Primary Endpoint(s)		
Secondary		
The secondary outcomes will include the two individual components of the BPI GPS: BPI pain severity and BPI pain interference.	BPI pain severity and BPI pain interference	The BPI assesses pain at its “worst,” “least,” “average,” and “now”. The BPI measures how much pain has interfered with seven daily activities, including general activity, walking, work, mood, enjoyment of life, relations with others, and sleep.
Tertiary		
We propose 4 tertiary outcomes to further assess the effect of the interventions on pain.	Global Rating of Change	GRC assesses overall clinical response. It is consistent with the IMMPACT recommendations for a 7-item patient global change scale ⁵⁹ . Modified to detect finer gradations of improvement, this scale is sensitive to treatment-related improvements ⁶⁰ .
	PROMIS pain intensity & PROMIS pain interference	PROMIS Adult Self-Reported Measures on physical health (fatigue, pain intensity, pain interference, physical function, sleep disturbance, pain behavior and sleep-related impairment) and social health (ability to participate in social roles and activities) (http://www.healthmeasures.net/explore-measurement-systems/promis/intro-to-promis). PROMIS measures were developed and validated with state of the science methods to be psychometrically sound (http://www.healthmeasures.net/explore-measurement-systems/promis/measure-development-research).

OBJECTIVES	ENDPOINTS	JUSTIFICATION FOR ENDPOINTS
	Chronic Pain Coping Inventory (CPCI)	Designed to assess the use of coping strategies that are typically targeted for change in multidisciplinary pain treatment programs, the CPCI can be used as a treatment outcome measure, as a screening measure, and to document the necessity of treatment.
Exploratory		
	Generalized Anxiety Disorder 7-item scale (GAD-7)	GAD-7 is a validated screening and severity measure for the most common anxiety disorders in primary care (i.e., generalized anxiety, panic, social anxiety, and post-traumatic stress disorder) ^{61,62} . Higher scores on GAD-7 represent more severe anxiety symptoms. Clinical anxiety is defined as GAD-7 score of ≥ 10 , a cut point validated in previous studies ^{61,62} .
	Patient Health Questionnaire 8-Item Depression Scale (PHQ-8)	PHQ-8 is a brief self-administered scale that assesses major depressive disorder core symptoms and allows a score (range: 0 to 24) based on the total number and severity of depressive symptoms noted over the previous two-week period. Its validity (including telephone mode of delivery), feasibility and capacity to detect changes of depressive symptoms over time are well established ⁶³⁻⁶⁶ . Clinical depression is defined as PHQ-8 score of ≥ 10 , a cut point validated in prior studies ^{65,67-69} .
	The Pain Catastrophizing Scale (PCS)	PCS is a 13-item scale that describes the catastrophic thoughts and feelings that people may have in response to pain. The psychometric properties of PCS are well established ⁷⁰⁻⁷² including sensitivity to change ^{73,74} . The total score ranges 0 (no catastrophizing) to 52 (severe catastrophizing).
	SF 36 physical function *	The Short Form 36 Health Survey Questionnaire (SF-36) is used to indicate the health status of particular populations, to help with service planning and to measure the impact of clinical and social interventions.
	PROMIS Adult measures: physical function, fatigue, social health, sleep disturbance, pain behavior	PROMIS Adult Self-Reported Measures on physical health (fatigue, pain intensity, pain interference, physical function, sleep disturbance, pain behavior and sleep-related impairment) and social health (ability to participate in social roles and activities) (http://www.healthmeasures.net/explore-measurement-systems/promis/intro-to-promis). PROMIS measures were developed and

OBJECTIVES	ENDPOINTS	JUSTIFICATION FOR ENDPOINTS
		validated with state of the science methods to be psychometrically sound (http://www.healthmeasures.net/explore-measurement-systems/promis/measure-development-research).
	Opioid Morphine Equivalent (OME)	OME is a measure of daily dose of opioid use. We will use self-reported opioid type ^{75,76} , medical record-based dosage and self-reported daily frequency to calculate the OME, reported in milligrams per day. The OME is calculated by multiplying dosage by daily frequency by a conversion factor for each opioid based on opioid strength ⁷⁷ .
	Health care service utilization	We will extract data on use of different allied health care services from date of enrollment until the one-year anniversary utilizing EMR. The general approach will include models for count data. Length of follow-up will be used as an offset. Poisson models will be used to estimate the mean number of events for each intervention group. Alternatively, negative binomial (NB) models will be used if there is evidence of over-dispersion in model diagnostics. The specific health care utilization measures include the following.
	PHQ Anxiety-Depression Scale (PHQ-ADS)	PHQ-ADS is a composite of PHQ-8 and GAD-7 scores. PHQ-ADS is a single measure for assessing psychological distress in clinical practice and research ⁷⁸ . This is especially salient given the frequent co-occurrence of depression and anxiety. PHQ-ADS cut points of 10, 20 and 30 were shown to represent mild, moderate, and severe levels of psychological distress, respectively. We are using cut point of ≥ 20 to represent moderate level of psychological distress.
	Frequency of Practicing Pain Coping Skills	Frequency of Practicing Pain Coping Skills . During the outcome data collection at weeks 13 and 25 we will ask participants how many days they practiced pain coping skills in the past 2 weeks (maximum of 14) ³ .
.	Others . The study will track medication use but will not control or restrict medication use as part of the study.	To assess co-intervention effect, a treatment survey will inquire about specific treatments the patient has received (opiates and other analgesics, psychotropic medications and use of complementary and integrative health modalities such as acupuncture) for pain since the last follow-up ⁶⁹ .

*We realize that the PROMIS Pain Interference and Pain Intensity are similar to BPI measures. However, the PROMIS measures are required of all NIH HEAL related projects. To reduce participant burden, we will drop SF-36 physical function (given that we already have PROMIS physical function).

4 STUDY DESIGN

4.1 OVERALL DESIGN

PRECICE is a 24-week RCT of patients in the primary care clinics. During the study, participants will be randomized to one of three treatments: (1) [duloxetine + web-based CBT] with health care professional support, vs. (2) [duloxetine + web-based CBT] without health care professional support, vs. (3) duloxetine only. The primary purpose of the phone-based health care professional support is to enhance participant's motivation to engage in the web-based CBT program with regular practice of newly learned pain coping skills during and after the study. See section 9 for the analytical plan including sub-group analyses.

4.2 SCIENTIFIC RATIONALE FOR STUDY DESIGN

We initially thought of a 3-arm study that compares combination treatment [duloxetine and web-based CBT] vs. duloxetine only vs. web-based CBT only. Such a design would allow us to also compare drug vs. web based CBT. We discarded the idea because it would be unethical to randomize participants with coexisting depression to a treatment arm (i.e., web-based CBT alone) without targeted treatment for depression. In addition, given the general tendency for practicing clinicians to prescribe medication, a more clinically relevant question would be, "What is the additional benefits of web-based CBT when offered concurrently with duloxetine?" Alternatively, a 2-arm RCT (duloxetine only vs. web-based CBT) would be a reasonable design, with combination treatment reserved for those who are non-responders to either duloxetine or CBT alone. However, we rejected this alternative for two reasons: (1) our primary goal is to optimize treatment outcome and a single agent would only yield minimal pain relief; and (2) initiating CBT earlier during treatment may prevent disability and further pain chronicity.

4.3 JUSTIFICATION FOR INTERVENTION

We realized that there are a few disadvantages in using a global endpoint: (1) they generally permit only global, not component-specific, conclusions and are subject to misinterpretation⁹³, and (2) treatment effects may be qualitatively different for different components of the composite^{93, 94}. Such an endpoint can thus mask a beneficial effect, or lack of effect for one or more of the components of the global endpoint. For this reason, the committee on the Initiative on Methods, Measurement, and Pain Assessment in Clinical Trials (IMMPACT) has recommended that analyses of each component of the BPI GPS should be reported as well⁹⁵. Thus, in the current application, we have put forth secondary hypotheses to examine the effects of combination treatment (duloxetine + web-based CBT) on the individual component of BPI pain severity and BPI pain interference as secondary endpoints.

4.4 END-OF-STUDY DEFINITION

A participant is considered to have completed the study if he or she has completed the baseline assessment at Week 0, activities associated with the randomized treatment arm, and assessments at Week 1, Week 13, and Week 25. We would consider a participant as having “complete” data if the BPI global pain severity (BPI-GPS) measure is collected at week 25. For further details, see Table 1 in section 1.3 Schedule of Activities. For a description of how we will handle missing data, see Section 9.4.2, “Analysis of the Primary Endpoint(s)”.

5 STUDY POPULATION

5.1 INCLUSION CRITERIA

In order to be eligible to participate in this study, an individual must meet all of the following criteria:

1. patients at the primary care clinic with daily pain for 3 months or longer affecting the low back, neck, hip, knee or widespread pain;
2. at least moderate in BPI GPS, defined as a GPS score of 5 or greater^{1,2}; and
3. at least age 18 years old or older.

5.2 EXCLUSION CRITERIA

An individual who meets any of the following criteria will be excluded from participation in this study:

1. uncontrolled hypertension - sitting systolic blood pressure >170 mmHg or diastolic blood pressure >100 mmHg at screening - (because duloxetine rarely increases blood pressure);
2. active suicidal ideation;
3. planned elective surgery during the study period (to avoid the confounding effect of possible complicated post-surgery recovery course on the primary outcome);
4. ongoing unresolved disability claims;
5. inflammatory arthritis (e.g., lupus and ankylosing spondylitis);
6. cancer-related musculoskeletal pain;
7. pregnancy;
8. history of bipolar disorder or schizophrenia;
9. narrow angle glaucoma;
10. participant reported chronic kidney disease stage 4, eGFR <30 and/or severe renal impairment (creatinine clearance <30);
11. current use of duloxetine;
12. current use of any of the following medications (to avoid adverse drug-to-drug interactions): tricyclic antidepressant > 25 mg daily dose, monoamine oxidase inhibitors, fluoxetine, sertraline, paroxetine, citalopram, escitalopram, venlafaxine, milnacipran, mirtazapine, , or aripiprazole, serotonin precursors (e.g., tryptophan), and strong CYP1A2 inhibitors (e.g., ciprofloxacin, other fluoroquinolones, fluvoxamine and verapamil);
13. poly-pharmacy (defined as concurrent daily use of 4 or more centrally acting medications for anxiety (anxiolytics), insomnia (hypnotics), anti-psychotic and anticonvulsants (gabapentin and pregabalin are permitted, if subject on a stable dose for at least 4 weeks).

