Duloxetine. We chose duloxetine as the first line drug because: (1) it has established efficacy for CMP and Food and Drug Administration (FDA) approval for that indication; and (2) it is available in generic form, which makes it more readily available. At study entry, all participants will receive duloxetine 30 mg once daily for one week; subjects who are able to tolerate 30 mg and do not have chronic kidney disease III (CKD-3) will increase to 60 mg once daily for 24 weeks. At week 25, participants will return to the research clinic for outcome assessments. At the last study visit (week 25), participants who would like to stop the medication, will be provided duloxetine 30 mg once daily for 7 days and medication treatment will then stop (tapering regimen). Subjects already taking 30 mg daily will stop dosing at their week 25 visit. Those who would like to continue duloxetine will be prescribed a 2-week supply of duloxetine and will be instructed to talk to their primary care provider (PCP). In addition, the investigator will send a Wake One message to the PCP to consider continuation of duloxetine.

Other treatments. The use of over-the-counter analgesic medications will be permitted and assessed to adjust for co-intervention differences between groups in the analyses.

For further details, see Section 6, Study Interventions or Experimental Manipulations.

Study Duration^{*}:

[figure not shown]
The estimated time from when the study opens to enrollment until completion of data collection is 45 months.

Participant Duration:

The time it will take for each individual participant to complete all study-related tasks is 25 weeks.

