1.3 SCHEDULE OF ACTIVITIES

Table 1. Study Measures and Time Points for Data Collection in PRECICE

Telephone Contacts/Visits ^a	Pre-Screening Visit	Week 0	Week 1	Week 2	Week 3	Week 4	Week 6	Week 10	Week 13	Week 14	Week 18	Week 22	Week 25	PRN
Type of Contact/Visit ^{b,c}	TC	IPV	IPV	TC	TC	TC	TC	TC	IPV	TC	TC	TC	IPV	PRN
Screening														
Phone Pre-Screening	✓													
Randomization			✓											
Physical Measures														
Blood Pressure	✓	✓							✓				✓	
Height	✓												✓	
Weight	✓												✓	
Urine Pregnancy Test	✓								✓					
Questionnaires														
3-item Pain Intensity Interview	✓								✓				✓	
Compiled Questionnaires		✓							✓				✓	
o Brief Pain Inventory														
o Generalized Anxiety Disorder (GAD-7)														
o Patient Health Questionnaire (PHQ8)														
o Global Rating of Change (GRoC)														
o Pain Catastrophizing Scale (PCS)														
o PROMIS Adult Self-Report														
o Chronic Pain Coping Inventory (CPCI)														
Demographics with Medical Diagnosis		✓												
Informed Consent		✓												
Missed Visit Form													✓	
Modified Pain Detect	✓													
Non-study Medication List	✓								✓				✓	
Nurse Counselling Tracking Form						✓		✓	✓		✓	✓	✓	
Opioid Risk Tool	✓													
Participant Status													✓	
Serious Adverse Event Report Form													✓	
Study Drug Accountability Log	✓ ^d	✓ ^e								✓			✓ ^f	
Study Medication Modification				✓						✓			✓ ^g	
Study Medication Symptom Monitoring Form		✓ ^h	✓ ⁱ			✓ ⁱ			✓ ⁱ		✓		✓ ^j	
TAPS – Tobacco, Alcohol, Prescription	✓												✓	
EMR Health Care Utilization ^h														

^a Weeks with participant contact are listed on this table.

^b IPV indicates in-person visit.

^c TC indicates telephone contact.

^d At study entry, all participants will receive duloxetine 30 mg once daily for one week.

^e At week 1, participants will receive duloxetine 60 mg once daily for 24 weeks.

^f At week 25, all participants will be provided duloxetine 30 mg once daily for 7 days and medication treatment will then stop (tapering regimen).

^g Phone administration on as needed basis only if participant calls the research office and complains of a potential side effect.

^h EMR Health Care Utilization will be collected at one year after randomization.

ⁱ Option of using text messaging as an adjunct to phone calls to assess duloxetine symptoms monitoring at weeks 2 and 4.

Revised 07/19/2021

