2. Second phase: This phase is devoted to strategies that strengthen commitment to practice newly learned pain coping skills regularly and consistently. Specifically, the third call would include helping the patient develop a plan for change (i.e. shift from why the patient should consider change to how the patient will make changes) communicating free choice, and reviewing consequences of adaptive vs. maladaptive pain-related behaviors. The fourth phone call would involve asking for a commitment to practice new skills and a plan worksheet.
3. Third phase: The last 2 calls are for follow-through strategies to prevent relapse. To review the changes that have occurred since the last session, the MI-trained health care professional will praise and reinforce any and all approximations of progress. He or she will also review behavioral indicators of motivation, patient's responses to questions concerning reasons for making or maintaining changes, and barriers to adherence. He or she will again obtain a commitment to follow through on the new plan.

Duloxetine. We chose duloxetine as the first line drug because: (1) it has established efficacy for CMP and FDA approval for that indication; and (2) it is available in generic form, which makes it more readily available.

At study entry, all participants will receive duloxetine 30 mg once daily for one week. At Week 1, subjects who tolerate the 30 mg daily dose and do not have chronic kidney disease stage 3 will begin 60 mg once daily for 24 weeks. Subjects with CKD-3 tolerating 30mg daily, will continue on 30mg for 24 weeks. At week 25, participants will return to the research clinic for outcome assessments.

To assure safety of study participants, subjects will complete a symptom monitoring form (formerly labeled as medication side effects checklist) at week 1, week 2, week 4, week 13 and week 25. The subject may be contacted via text messaging as an adjunct to phone calls to assess duloxetine symptoms

monitoring at weeks 2 and 4 and for appointment reminders. The medical safety officer will be informed of any AEs (at week 1, week 2, week 4, week 13 and week 25) that require medical attention. For AEs that require medical attention, the study Medical Safety Officer will directly contact the participant to provide immediate care and guidance.

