At the last study visit (week 25), participants who would like to stop the medication will be provided duloxetine 30 mg once daily for 7 days and medication treatment will then stop (tapering regimen). Subjects already taking 30 mg daily will stop dosing at their week 25 visit. Those who would like to continue duloxetine will be prescribed a 2-week supply of duloxetine and will be instructed to talk to their primary care provider (PCP). In addition, the investigator will send a Wake One message to the PCP to consider continuation of duloxetine.

Other treatments. The use of over-the-counter analgesic medications will be permitted and assessed to adjust for co-intervention differences between groups in the analyses.

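### Table 1 footnotes e and f contradict the duloxetine dosing rules in section 6.1.1; secondarily, the protocol names no required record source for the kidney status that sets the dose

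*Combined protocol and SAP*

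**What the plan says.** **Dosing in the text.** Under the synopsis, participants who tolerate 30 mg and "do not have chronic kidney disease III (CKD-3) will increase to 60 mg once daily for 24 weeks". Section 6.1.1 has the same rule and adds: "Subjects with CKD-3 tolerating 30mg daily, will continue on 30mg for 24 weeks". At Week 25, 6.1.1 has three rules: those who want to stop get a 7-day taper at 30 mg; "Subjects already taking 30 mg daily will stop dosing at their week 25 visit"; and those who want to continue get a 2-week supply and are referred to their primary care provider. Section 6.1.2 sends the reader to 6.1.1 for dosing and to chapter 09 of the Manual of Procedures (MOP) for further detail.

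**Dosing in Table 1.** Footnote e reads: "At week 1, participants will receive duloxetine 60 mg once daily for 24 weeks". Footnote f says that at Week 25 "all participants will be provided duloxetine 30 mg once daily for 7 days and medication treatment will then stop". Both hang on the row for the study drug accountability log.

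**Kidney status.** Exclusion 10 in section 5.2 reads "participant reported chronic kidney disease stage 4, eGFR <30 and/or severe renal impairment (creatinine clearance <30". Neither the synopsis nor 6.1.1 says how CKD-3 is established. Table 1 lists no creatinine or eGFR. It has a Week 0 form titled "Demographics with Medical Diagnosis", with no data source stated. Section 2.3.1 says the study adds no tests and that a participant's "study doctor may capture results of testing performed for normal clinical care".

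**The concern.** Dose instructions for the same participant at the same visit should not depend on which page staff open. Here they do. Table 1 is the page that sections 4.4, 6.4 and 8.1 send readers to for study activities, and its footnotes sit on the drug log. Someone working from it would step a CKD-3 participant up to 60 mg, against a rule whose stated rationale in the amendment history (section 10.4, Version 8) is safety. At Week 25 the same reader would hand a further week of drug to people who should stop, and would end treatment for people entitled to continue.

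The kidney question compounds this. Version 8 admitted CKD-3 patients to help recruitment, so separating stage 3 from stage 4, and from no kidney disease, now decides both eligibility and dose. Exclusion 10 uses laboratory cut-offs, yet nothing in the supplied text requires anyone to look for a kidney value or diagnosis in the record before the dose is raised. A participant unaware of reduced kidney function could be enrolled or stepped up against the protocol's intent.

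**Working it through.** There is no plan figure to reproduce. The check sets the two sets of instructions side by side for each group of participants.

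| Participant | Table 1 footnote | Section 6.1.1 | Result |
|---|---|---|---|
| Week 1: no CKD-3, tolerates 30 mg | e: 60 mg | 60 mg | agree |
| Week 1: CKD-3, tolerates 30 mg | e: 60 mg | 30 mg | conflict |
| Week 1: does not tolerate 30 mg | e: 60 mg | not stepped up | conflict |
| Week 25: on 60 mg, wants to stop | f: 30 mg for 7 days, then stop | 30 mg for 7 days, then stop | agree |
| Week 25: already on 30 mg | f: 30 mg for 7 days, then stop | stop at the visit | conflict |
| Week 25: wants to continue | f: 30 mg for 7 days, then stop | 2-week supply and referral | conflict |

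Size of each conflict, from the protocol's own doses:

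- CKD-3 at Week 1: 60 / 30 = 2 times the intended daily dose.
- Already on 30 mg at Week 25: 7 further days of drug against 0.
- Wishing to continue: 7 days and then none, against 2 × 7 = 14 days and a handover.

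**Likely cause.** Table 1 is stamped 07/19/2021. CKD-3 dosing came with Version 8 on 11/01/2022, so footnote e appears not to have been updated for it. That does not explain all of footnote f: the 2-week supply came with Version 4 on 01/14/2021, before the stamp. The dates only suggest how the conflict arose; the conflict itself lies between two parts of the current text.

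**Kidney source.** The provisions that might supply a check are:

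- the Week 0 diagnosis form;
- validation that eligibility criteria were tested (8.2, item 6b);
- symptom monitoring with medical safety officer review (8.2, item 4);
- management changes after a clinically significant finding (7.1);
- discontinuation for an exclusion recognised late (7.2);
- entry of clinical laboratory data into REDCap (10.1.9.1).

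Each is general. None requires a kidney value or CKD diagnosis from the record before dispensing or step-up.

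**The case against.** On the footnotes, the best reply is that the synopsis and 6.1.1 agree in detail, and 6.1.2 names 6.1.1 as the place for dosing, so a careful reader is not misled. That lowers the risk of error. It does not make two opposite instructions consistent, and the wrong one sits on the drug log row. A reader might infer that CKD-3 participants are actually being given double the dose. The documents do not support that: they show a wrong instruction, not that anyone followed it in preference to 6.1.1.

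On kidney status, the reply is stronger. Participant report is an express choice in a Phase 4 primary-care trial that adds no tests, and exclusions 8, 9 and 12 name no source either. MOP chapters 02 and 09, cited in 5.5 and 6.1.2, were not supplied and may already contain a check. A reader might infer that the whole renal exclusion rests on self-report with nothing behind it. That goes too far. The reporting phrase may govern only stage 4 disease, in which case the eGFR and creatinine clearance limits simply have no named source, and the general safeguards could still catch some cases. What stands is narrower: on either reading, the supplied protocol requires no kidney-specific look at the record, although CKD-3 status decides the dose.

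**Conclusion.** Footnotes e and f are wrong as written. For a CKD-3 participant, footnote e gives twice the daily dose that 6.1.1 intends, and it ignores intolerance of 30 mg. Footnote f misdirects both those already on 30 mg and those who wish to continue. This rests only on the current text and is certain.

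The missing record source is a secondary point and holds only if the MOP does not already supply one. The documents do not say how many participants have CKD-3 or unrecognised kidney disease, nor what harm 60 mg would do them, so neither the number affected nor the harm can be estimated. Nothing here changes the sample size, the power or the as-randomized primary analysis.

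**What to change.** **Footnotes (editorial, no cost in data or visits).**

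- Footnote e: participants who tolerate 30 mg and do not have CKD-3 receive 60 mg once daily for 24 weeks; those with CKD-3 who tolerate 30 mg remain on 30 mg.
- Footnote f: state the three Week 25 rules of 6.1.1, namely taper for those on 60 mg who wish to stop, stop at the visit for those already on 30 mg, and a 2-week supply for those who wish to continue.

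**Kidney status.** If the MOP already requires a record check, cite the chapter in 5.2 and 6.1.1. If not, have existing staff look for any available eGFR, creatinine or CKD diagnosis in the accessible record, after consent and before the Week 1 step-up. Where a record is absent or still pending, use participant report flagged to the medical safety officer, so that an unanswered query does not hold up the visit. Thresholds and doses stay as they are. Anyone found ineligible before randomization is a screen failure under 5.4. A randomized participant found on the wrong dose is corrected and by default stays in follow-up under 7.1.

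**Cost.** No new test or visit is needed, and 8.2 already allows record access after consent. Staff time, with every input assumed:

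- If 10% to 30% leave before 280 are randomized, 280 / 0.90 = 311 to 280 / 0.70 = 400 people are checked.
- At 5 to 10 minutes each: 311 × 5 / 60 = 25.9 to 400 × 10 / 60 = 66.7 hours.
- A further 15 minutes of query or safety officer review for 10% to 30% of them: 311 × 0.10 × 15 / 60 = 7.8 to 400 × 0.30 × 15 / 60 = 30.0 hours.
- Total: about 34 to 97 hours over the whole trial, and less if only remaining enrolment is covered.

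A few participants would be excluded or held at 30 mg. Some records will be old or missing, and because consent and first dispensing both fall at Week 0, someone found ineligible at Week 1 may already have taken a week of 30 mg.
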